4.0 Enrollment/Randomization

We will use the 3-stage process of our past trials to recruit patients. First, the Regenstrief Medical Records System,¹⁶⁶ one of most comprehensive electronic medical records, will be searched in accordance with HIPAA to generate lists of eligible patients. Next, ResNet assistants will obtain permission to approach from each patient's provider. ResNet, Indiana University's primary care practice-based research network, is the sole mechanism through which patients in the targeted clinics can be contacted for research. ResNet also maintains a patient registry, which will also be used by ResNet to identify potentially eligible patients. Finally, ResNet assistants will conduct high-intensity in-clinic and telephone screening and will enroll eligible patients (see Appendix 1 for Screening Interview). ResNet assistants will use a paper copy or a REDCap version of the Screening Interview. Through administering the eligibility interview refined in our pilots, ResNet assistants will assess cognitive function, medical/psychiatric status, and depression status; will obtain consent and authorization; and will implement the suicidal ideation protection protocol.

We estimate that $\approx 4,320$ patients (45/week) will need to be approached, consistent with the IMPACT trial.³⁶ We will be able to start recruitment immediately, as the infrastructure, personnel, and protocols are in place from the PI's recent trials. At the Indiana sites of the IMPACT trial, 6.4% of approached patients were randomized. We conservatively estimate that 5% of approached patients will be randomized (9/month) in the proposed trial. Patients who meet inclusion/exclusion criteria and consent will be scheduled for the pre-treatment visit. Because only patients who attend this visit will be randomized, it will serve as a prerandomization compliance screening.¹⁶⁷

In the unanticipated event of slower-than-projected recruitment, we will first request direct referrals from providers in the targeted clinics. Next, we will pursue expanding recruitment to another healthcare system in Indianapolis, such as the VAMC or Community Health Network. Finally, we will extend the recruitment window up to a year if the benefits to the primary outcome of endothelial dysfunction (ample power due to a larger sample) outweigh the costs to the exploratory outcome of CVD events (shorter observation period).

At the end of the pre-treatment visit described below, the randomization procedure will be initiated. To balance the groups on two strong FMD correlates,⁹¹ randomization will be stratified by sex and age (50-59 and 60+ years) using random number sequences.¹⁶⁸ Sequentially numbered sealed envelopes containing group assignment will be prepared by the study statistician ([name]).

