Patients will undergo FMD assessments at [name] laboratory in accordance with consensus guidelines.⁸¹ [name] as well as [name] and [name] (our vascular ultrasonographers) have undergone certified training through the University of Wisconsin Brachial Artery Reactivity Testing Symposium. Our group has performed 700+ FMD assessments in the past 10 years. We utilize a GE Logiq E ultrasound system with AccessPoint 2011 software. To illustrate the reproducibility of our results, we performed paired FMDs over 1-4 weeks in 11 healthy volunteers in 2013. Intraclass correlations for baseline diameter, reactive hyperemia, and FMD were 0.98, 0.98, and 0.70, which compare favorably to other laboratories.¹⁸¹⁻¹⁸³

After a 10-minute supine rest, high-resolution baseline images of the brachial artery will be obtained from 3 consecutive cardiac cycles. Next, the forearm cuff will be inflated to 250 mmHg for 5 minutes and then rapidly deflated. At 60 and 90 seconds post deflation, images from 3 consecutive cardiac cycles will be acquired. Brachial diameters will be measured at peak R wave. FMD values will be computed as % increase in diameter at 60 or 90 seconds post deflation^{196,197} (the larger of the two values). Percent change in reactive hyperemic flow velocities will also be computed to ensure that sufficient shear stress triggers were induced.

Atherogenic Physiologic Factors (Secondary Outcomes)

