8.0 Statistical Considerations

Sample Size and Power Considerations

Endothelial Dysfunction

Using the effect size of depression treatment on FMD from our pilot trial, we need 88 patients (44 per arm) to detect a group difference in FMD of 1.7% ($d = 0.61$) at 12 months, assuming a power level of 0.80 and a Type I error of 0.05. This would be a clinically relevant difference. Assuming a conservative attrition rate of 20%,²⁰⁴ we will have 172 completers ($220 \times .80$) for FMD, yielding power levels of 0.98 for $d = 0.61$ and 0.80 for $d = 0.43$.

Candidate Mechanisms

We expect at a power level ≥ 0.80 for the candidate mechanisms (Hypotheses 2-5), as we will be able to detect effect sizes as small as $d = 0.43$ with 172 completers. In our IMPACT study³⁵ and pilot trial, effect sizes for depressive symptoms ($d = 0.69$ and 1.33), IL-6 ($d = 0.43$), and CRP ($d = 0.78$) were in the medium-to-large range. In other studies, effect sizes of 0.52 were found for psychological interventions on heart rate variability,²⁰⁵⁻²⁰⁷ 1.00 for SSRIs on IL-6,¹⁴³ 0.74 for SSRIs¹⁴³ and 0.85 for CBT¹³⁸ on CRP, 0.91¹⁴⁶ and 0.46¹⁴⁴ for SSRIs on BTG, and 0.87 for SSRIs on PF4.¹⁴⁴

CVD Events

Over the mean observation period of 4 years, we anticipate a cumulative CVD event rate of 20% (39 events) and a 25% lower relative risk ($HR \leq 0.75$) in eIMPACT versus usual care. These estimates are reasonable, as we observed a CVD event rate of 24% and a 46% lower relative risk (event rate: 18% vs. 31%) in our IMPACT secondary analysis that had a 4-year observation period. Our high-risk sample will differ from the typical sample of a risk reduction trial in that (a) all patients will have depression and ≥ 1 CVD risk factor and (b) many will be of low SES and/or African American, two groups at elevated risk for CVD event.^{1,171} Although we expect to have CVD event data for nearly all patients, we assume a conservative attrition rate of 10%, leaving 194 completers. As is typical of Phase 2 trials, our trial is not designed to detect a statistically significant difference in clinical events; however, a 25% relative risk reduction would be a clinically relevant signal (statin therapy reduces risk by $\approx 30\%$ ¹⁵⁶) and has been used to power recent event-driven Phase 3 cardiology trials.¹⁵⁷

Statistical Analyses

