We will use the intent-to-treat approach.²⁰⁸ All tests will be two-tailed with $p < .05$ considered significant. Supplemental analyses of completers will be performed. We will assess for differences in all baseline factors. Due to randomization, we do not expect baseline group differences. Even so, any differences will be taken into account when interpreting results, and any baseline factors that differ between the groups will be included as covariates in sensitivity analyses. Aim 1: We will test our hypothesis that eIMPACT patients will exhibit greater improvement in endothelial dysfunction (Hypothesis 1) by performing a two-sample t-test with FMD at 12 months as the dependent variable. If there is a group difference in baseline FMD, analyses of covariance (ANCOVAs) adjusting for baseline level will also be performed. We will also explore whether eIMPACT patients show a clinically relevant reduction (25% lower relative risk) in CVD events by running a Cox proportional hazards model with treatment group predicting time to first CVD event. Patients will be censored at non-CVD death or the end date. We expect to observe a $HR \leq 0.75$. Aim 2: We will test our hypotheses that eIMPACT patients will exhibit greater decreases in the candidate mechanisms (Hypotheses 2-5) by performing two-sample t-tests with SCL-20 score, high-frequency heart rate variability, IL-6, CRP, BTG, and PF4 at 12 months as the dependent variables. If baseline group differences are found, ANCOVAs adjusting for baseline level will

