also be performed. To explore whether decreases in the candidate mechanisms are associated with improvements in endothelial dysfunction, we will compute correlations between 12-month change in each mechanism and in FMD. To explore whether decreases in the candidate mechanisms are partial mediators of eIMPACT's hypothesized cardioprotective effect, we will conduct exploratory mediation analyses using MacKinnon's approach, which has greater power than others.²⁰⁹ First, to quantify the treatment effect on each mechanism ("a" coefficients), we will perform linear regressions with treatment group predicting 12-month level of each mechanism. Second, to quantify the effect of each candidate mechanism on endothelial dysfunction ("b" coefficients), we will perform linear regressions with 12-month level of each mechanism predicting 12-month FMD in the presence of treatment group. Third, the significance of each mediation effect will be tested using MacKinnon and Lockwood's product of coefficients ("ab") method employing asymmetric confidence limits.^{209,210} If this test is significant, the selected mechanism is a partial mediator of the treatment effect on 12-month FMD. Of note, we will also explore (a) if changes in depressive symptoms are correlated with changes in the atherogenic physiologic factors and (b) if changes in FMD predict CVD events.

Supplemental, Hypothesis-Generating Analyses

(1) We will explore atherogenic behavioral factors, conventional CVD risk factors, and depression care variables as potential mechanisms of eIMPACT's effect on FMD by repeating Aim 2 analyses. (2) To explore the separate effects of intervention components (which likely have shared and unique pathways; Figure 1), Aim 1 and 2 analyses will be repeated after coding the treatment variable as follows: eIMPACT both components, eIMPACT antidepressants only, eIMPACT psychotherapy only, eIMPACT neither component, and usual care. (3) We will explore sex and race/ethnicity as moderators of the treatment effect on the outcomes. (4) We will estimate the cost per patient of providing eIMPACT, including charges for BtB, DCS, psychiatrist and primary care expert supervision, materials, and a telephone line.

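### Sex and age group are stratified as FMD correlates but left out of the unadjusted primary t-test: a small loss of precision with no bias, and mild conservatism only if allocation is blocked

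*Combined protocol and SAP*

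**What the plan says.** Section 4.0 (Enrollment/Randomization) gives the reason for stratifying, "To balance the groups on two strong FMD correlates", and the method: "randomization will be stratified by sex and age (50-59 and 60+ years) using random number sequences". Assignments are held in sequentially numbered sealed envelopes. No blocking, block size or other balancing device is stated.

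Section 8.0 (Statistical Analyses, Aim 1) tests Hypothesis 1 by "performing a two-sample t-test with FMD at 12 months as the dependent variable". Treatment is the only predictor. Two conditional rules follow:

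- For baseline FMD: "If there is a group difference in baseline FMD, analyses of covariance (ANCOVAs) adjusting for baseline level will also be performed".
- For other variables: "any baseline factors that differ between the groups will be included as covariates in sensitivity analyses".

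Under both rules the extra analysis sits beside the t-test and does not replace it. Among the supplemental analyses, sex appears once more: "We will explore sex and race/ethnicity as moderators of the treatment effect on the outcomes". Age group does not reappear.

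**The concern.** The plan treats sex and age group as important enough predictors of the primary outcome to build them into the randomisation, then ignores them in the primary test. The imbalance rules do not repair this. Stratification is meant to make a difference in sex or age group unlikely, so those rules would seldom admit them. In any case, a covariate adds precision because it predicts the outcome, whether or not the arms happen to differ on it.

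Two things are at stake. One is the width of the interval for the primary effect, which Section 1.0 wants as an input to a Phase 3 design. The other is calibration: if allocation is balanced within strata, the t-test's standard error still includes between-stratum variance that the design has removed from the treatment comparison.

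**Working it through.** **Inputs from the plan (Section 8.0).** Difference 1.7 FMD points, d = 0.61, so SD = 1.7/0.61 = 2.79. Two-sided alpha 0.05. 172 completers. (The plan's own product, 220 × 0.80, is 176; using 176 changes power by less than 1 point.)

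**Assumptions (not in the plan).** R² is the share of 12-month FMD variance explained by sex and age group: 0.05, 0.10 or 0.20. The correlation r between baseline and 12-month FMD is 0.5 or 0.7.

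**1. The plan's own figures.** A two-sample t-test needs 43.2 per arm, rounded up to 44, as stated. In SD units the standard error is √(4/172) = 0.1525. Power is Φ(d/0.1525 − 1.96), which gives 0.979 at d = 0.61 and 0.805 at d = 0.43. The noncentral t gives 0.978 and 0.801. The stated 0.98 and 0.80 are reproduced.

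**2. Precision from the strata alone.** The unadjusted half-width is 1.974 × 0.1525 × 2.79 = 0.84 FMD points. Adjustment multiplies it by √(1 − R²). Adjusted power is Φ(d/(0.1525√(1 − R²)) − 1.96).

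| R² | Half-width | Power, d = 0.43 | Power, d = 0.61 |
|---|---|---|---|
| 0 (unadjusted) | 0.84 | 0.805 | 0.979 |
| 0.05 | 0.82 | 0.825 | 0.984 |
| 0.10 | 0.80 | 0.844 | 0.988 |
| 0.20 | 0.75 | 0.883 | 0.994 |

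**3. Calibration.** A simulation used 220 randomised, 48 lost at random and 40,000 runs per cell.

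- Blocks of 4 within strata: t-test type I error was 0.046, 0.041-0.042 and 0.033-0.035 for the three R² values, with a standard error about 2-9% too wide. Power at d = 0.43 was 0.80-0.82 unadjusted and 0.82-0.88 adjusted for strata.
- Unrestricted allocation within strata: type I error was 0.049-0.051. Power at d = 0.43 was about 0.80 unadjusted and 0.81-0.88 adjusted.
- Both schemes at d = 0.61: 0.976-0.986 unadjusted, 0.980-0.993 adjusted.

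A second, independent simulation agreed (blocked type I error 0.048, 0.043, 0.031) and found the unadjusted estimate unbiased, its mean within 0.002 SD of the truth. With exact balance among those analysed, type I error would be 2(1 − Φ(1.96/√(1 − R²))) = 0.044, 0.039, 0.028; random dropout loosens the balance and softens the effect.

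**4. What the strata add once baseline FMD is in the model.** With baseline FMD alone the residual variance is 1 − r². If the strata act equally at both visits, adding them gives (1 − R²)[1 − ((r − R²)/(1 − R²))²]. Power at d = 0.43:

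| r | Baseline FMD only | + strata, R² = 0.05 | 0.10 | 0.20 |
|---|---|---|---|---|
| 0.5 | 0.903 | 0.907 | 0.913 | 0.925 |
| 0.7 | 0.977 | 0.978 | 0.979 | 0.981 |

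Baseline FMD lifts power from 0.805 to 0.903 or 0.977. The strata then add under 0.5 points at r = 0.7. The gain reaches about 2 points only at r = 0.5 with R² = 0.20, where the strata would have to explain 0.20/0.50 = 40% of the FMD variance shared between visits. The simulation gave the same picture (0.903 to 0.920 and 0.976 to 0.979, blocked).

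**5. Plausibility of the R² range.** Section 5.0 reports: "Intraclass correlations for baseline diameter, reactive hyperemia, and FMD were 0.98, 0.98, and 0.70". That comes from 11 healthy volunteers over 1-4 weeks. If 0.70 applied here, R² = 0.20 would need sex and one age cut to explain 0.20/0.70 = 29% of stable FMD variance; R² = 0.05 would need 7%. The upper end of the range is demanding.

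**The case against.** The strongest reply is that nothing the plan claims fails. A t-test after stratified randomisation is valid, the power figures reproduce, and under blocking the unadjusted test has at least its stated power at these effects. The planning effect is d = 0.61, where adjustment hardly matters; the visible gains are at d = 0.43, the smallest effect detectable with 0.80 power. R² is unknown, blocking is unstated, and most of the benefit of the proposed model comes from baseline FMD rather than the strata. All of this stands, and it limits the point to a minor one.

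It does not remove the point. The covariates are already collected, the plan itself calls two of them strong correlates, and fixing the model in advance ends a data-dependent choice: Section 8.0 neither defines a baseline difference nor says which result governs if the t-test and ANCOVA disagree.

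A reader might infer more than the documents support:

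- That the primary test is biased or invalid. Omitting the strata does not bias the comparison. Dropout that depends on sex or age differently by arm could, but that is a missing-data question.
- That the t-test is certainly conservative. This requires restricted allocation within strata, which Section 4.0 does not state. Without it, type I error is nominal.
- That the stated power is wrong. It is not.

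**Conclusion.** The point holds as a minor matter of efficiency and reporting. The size of the loss rests on an assumed R² of 0.05-0.20. On that range the primary interval is wider than it need be by 0.02-0.09 FMD points on each side (0.84 against 0.82-0.75), and power at d = 0.43 is about 0.80-0.82 where strata adjustment alone would give 0.81-0.88. At d = 0.61 it is about 0.98-0.99 either way. Any miscalibration is in the conservative direction and arises only under blocked allocation, with type I error about 0.046-0.034. Given baseline FMD in the model, the strata contribute about 0-0.5 power points at d = 0.43 if the two visits correlate at 0.7, and about 2 points only in the extreme case described above.

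**What to change.** Before outcome data by arm are seen, pre-specify the primary analysis as a linear model for 12-month FMD with treatment, baseline FMD, sex and age group (50-59, 60+), fitted regardless of observed balance. The unadjusted t-test can be kept as a supporting analysis. State in Section 4.0 whether allocation within strata is blocked.

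Use the same covariates in the Aim 2 mediation regressions in which 12-month FMD is the outcome, so that models for the same outcome agree. No change is proposed for the Aim 2 tests with other outcomes or for the Cox model, since Section 4.0 supports the strata only as correlates of FMD.

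The cost is SAP wording and about three degrees of freedom (baseline FMD, sex, age group) out of about 170, with no new data. The one constraint is timing: a change of primary test must be fixed and dated before results by arm are available.

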5.0 Study Procedures

Overview, Visits, and Setting

We will conduct a Phase 2 randomized controlled trial of 220 primary care patients aged 50+ years with a depressive disorder and CVD risk factors but no clinical CVD. Patients will be randomized to 12 months of eIMPACT, our modernized IMPACT intervention, or usual care and will be followed for a mean of 4 years.

The timing of activities is shown in the table below. We will strive to schedule patients within two weeks of enrollment, although some visits will fall outside of that window due to conflicts in the patients' schedules and no-showed or rescheduled appointments. Patients will attend a 3-hour pre-treatment visit at the Indiana CTSI Clinical Research Center. To minimize the effect of extraneous factors on FMD,^{169,170} patients will be told to fast and to avoid tobacco and exercise for ≥ 8 hours before their visit. The exam room will be kept at 68-71°F, and premenopausal women will be scheduled within 2 weeks of menstruation onset. Patients will have their height, weight, and BP measured; will complete self-report scales on a secure SurveyMonkey website designed for this study visit; and will undergo FMD and heart rate variability assessments and a blood draw (standard venipuncture). To end this visit, the randomization procedure will be initiated, the patient and the treatment team will be notified of the assignment, and the mid-treatment call and post-treatment visit will be scheduled. If the patient is randomized to the eIMPACT intervention, the depression clinical specialist will conduct a brief session over FaceTime to orient the patient to intervention materials and to schedule the initial assessment. The FaceTime session will not be recorded. Within 2 weeks, the depression clinical specialist will call eIMPACT patients to initiate treatment, and a research assistant will send a letter to the primary care providers of usual care patients to notify them that their patient has a depressive disorder and to encourage follow-up. Approximately six months after randomization, research assistants will contact all patients to complete the 45-min mid-treatment call. First, a brief questionnaire used in our pilot trials will be administered to assess for the occurrence of CVD events since enrollment. As we have also done in our pilot projects, the self-reported scales completed at pre-treatment will then be readministered. Approximately twelve months after randomization, patients will return to the Clinical Research Center for the post-treatment visit, during which all factors measured at pre-treatment will be reassessed. Finally, research assistant will contact patients annually after their post-treatment visit to complete the follow-up calls, with the last call coming within 2 weeks of the study end date. These calls will follow the same procedures as the mid-treatment call.

The schedule of participant reimbursement is as follows: \$100 for the pre-treatment visit, \$25 for the mid-treatment call, \$100 for the post-treatment visit, \$20 for each of the annual follow-up calls, and up to \$10 per visit to cover parking or transportation costs.

	Year 01			Year 02			Year 03			Year 04			Year 05		
Recruitment & Pre-Treatment Visits															
Treatment															
Mid-Treatment Calls															
Post-Treatment Visits															
Annual Follow-Up Calls															
Analysis & Manuscript Submission															

The setting, which is identical to the IMPACT trial, is the primary care clinics of two healthcare systems affiliated with Indiana University: Eskenazi Health and Indiana University Health. Eskenazi Health, a safety net

healthcare system, provides care for ≈20% of the population of Indianapolis. The Eskenazi Health Center for Senior Health, where elderly patients receive primary care, is included in the targeted clinics. About 90% of Eskenazi patients are underinsured or uninsured, and 50% are African American. Therefore, these patients provide special opportunities to research diseases that disproportionately affect lower SES and minority populations, such as CVD.^{1,171} Indiana University Health, a large academic medical center, is Indiana's most comprehensive healthcare system.

Treatment Groups

eIMPACT

eIMPACT is a collaborative stepped care intervention involving a multidisciplinary team delivering evidenced-based treatments consistent with patient preference. We will modernize the IMPACT intervention (a) by adding a computerized CBT as the first-line psychotherapy and (b) by delivering some of the other components via telephone or FaceTime (see below). None of the computerized, telephonic, or FaceTime sessions will be recorded. Other than restricting the list of antidepressant medications to maximize CVD risk reduction, the remaining IMPACT components will not be altered.

Beating the Blues (BtB; Ultrasis PLC) is a widely used, empirically supported, stand-alone CBT program for depression designed for primary care patients and appropriate for adults with little computer experience and a 5th-6th grade reading level.⁶⁶ In prior trials, we have used the UK and US versions; we will use the US version in the proposed trial (see www.beatingthebluesus.com for a brief video tutorial). BtB utilizes an interactive, multimedia format to deliver eight 50-minute, weekly sessions, the structure and content of which mirror face-to-face CBT. Although sessions are tailored to each patient's problems, general topics include challenging dysfunctional thoughts, activity scheduling, problem solving, graded exposure, task breakdown, sleep management, and relapse prevention. Patients are also assigned tailored homeworks.

To minimize treatment barriers (e.g., transportation issues) and attrition, to reduce subject burden, and to ultimately facilitate implementation of eIMPACT, BtB sessions will occur in a private room at the Clinical Research Center, at [name] laboratory, at the patient's primary care clinic, or in a location selected by the patient where s/he can access a computer with internet, such as the patient's home, the patient's work, a family member's/friend's home, or a public library. Patient preference will drive the location decision. Patients will be offered with ear bud headphones if they plan to use them at remote locations and do not already own a pair that they would rather use. All patients completing BtB will be provided with a BtB binder that contains printouts of all BtB worksheets.

To begin each in-person BtB session, an assistant will collect the homework. The patient will then work alone through the BtB session at his/her own pace, with the assistant providing help only with technical issues. To end the session, the assistant will give the patient the printed homework.

Remote BtB sessions will be scheduled, just like in-person sessions. To begin each remote BtB session, an assistant will call the patient to instruct the patient to put last week's homework in the BtB binder, to address any technical issues, and to ensure that the patient has launched the correct BtB session for that day. The patient will then work alone through the BtB session at his/her own pace, with the assistant monitoring progress remotely on the secure BtB website set up for this trial. To end the session, the assistant will call the patient back to address any questions and ensure that the patient has identified the correct printed homework in the BtB binder.

Problem Solving Treatment in Primary Care (PST-PC) is a manualized, empirically supported CBT developed for use by healthcare professionals in primary care.¹⁷²⁻¹⁷⁷ The focus of the 6-10 30-minute sessions is teaching patients approaches for solving current problems contributing to depression. PST-PC was the first-line therapy in the IMPACT trial; however, it is our second-line therapy. We will deliver PST-PC primarily via telephone or FaceTime (although in-person sessions are also allowed), which Davidson et al.⁶⁰ found to be feasible and efficacious in the recent CODIACS Vanguard trial. Our consultant ([name]) also completed the Bypassing the Blues trial in which his team delivered collaborative depression care to cardiac patients via telephone and observed positive results.⁶³

The IMPACT treatment manual provides guidelines for using antidepressants, such as selecting a medication, titrating, switching to another medication, managing side effects, and avoiding drug interactions.⁶⁵ To optimize eIMPACT for CVD risk reduction, we have restricted the IMPACT list of antidepressants to SSRIs, duloxetine, bupropion, and mirtazapine. These medications are FDA approved for the treatment of depression and are the safest from a cardiovascular perspective.^{178,179} We are prohibiting the use of most serotonin-norepinephrine reuptake inhibitors (SNRIs) and all tricyclics due to their potential adverse effects on cardiovascular parameters.^{178,179} We do not expect this change to have a negative effect on depression outcomes, as antidepressants not on our list of allowed medications are typically used only as second- or third-line treatments and also have contraindications.⁶⁵

At the first session, the depression clinical specialist (DCS), a Master's-level licensed mental health counselor (LMHC), will review depression materials and discuss treatment options. The DCS will then work with the patient's primary care provider to develop a plan that follows the IMPACT algorithm⁶⁵ with modifications noted above. Our modernized algorithm recommends a Step 1 treatment of 8-12 weeks of BtB or an antidepressant depending on the patient preference. Providers will manage prescriptions. In addition to delivering PST-PC, the DCS will help the patient adhere to antidepressant therapy and schedule pleasurable activities. If the patient is taking an antidepressant at baseline, the dose will be increased, BtB will be added, or the antidepressant will be discontinued and another one will be prescribed or BtB will be delivered. If the patient wants psychotherapy but has a strong preference for traditional treatment, PST-PC will be offered at Step 1. The DCS will have weekly team meetings with the supervising psychiatrist ([name]) and primary care expert ([name]), during which new cases and those requiring plan changes will be discussed. Fidelity to the eIMPACT algorithm will be continually assessed and recorded by the supervisors at these team meetings, and adjustments needed to ensure high fidelity will be made.

The DCS will follow patients for 12 months, while monitoring response.¹⁵⁸ At the start, the DCS will attempt to have telephone sessions or contacts at least every 2 weeks. For patients who achieve remission ($\geq 50\%$ PHQ-9 reduction and < 3 MDD symptoms³⁶), the DCS will develop a relapse prevention plan and follow up monthly. Step 2 treatment – which involves either augmenting Step 1 treatment with an antidepressant or psychotherapy or switching to another antidepressant or psychotherapy – will be delivered to patients who do not achieve remission. If a patient does not respond after 6-10 more weeks, Step 3 treatment will be initiated, which consists of additional medications and psychotherapy, hospitalization, or other services. In the IMPACT trial,³⁶ intervention patients had 9.2 ± 6.2 in-clinic sessions and 6.1 ± 5.1 telephone contacts with a DCS during the 12 months of treatment. At the end of the 12 month treatment phase, the participant will receive a certificate indicating completion of eIMPACT treatment. We expect similar numbers in our trial, although most sessions/contacts will be via telephone. Based on our experiences, one DCS can manage 80-100 patients. The maximum number of patients in treatment at any given time in this trial will not exceed 80.

Usual Care

This arm was modeled after the IMPACT trial control group.³⁶ At the pre-treatment visit, patients will be informed of their depression diagnosis and group assignment, will be provided with a list of local mental health services (with contact information) available to Eskenazi patients, and will be encouraged to follow-up with their primary care provider regarding their depression. These patients will also be reminded (from the informed consent statement) that, although we will pass along information to their primary care provider, participants in this group do not receive any depression treatment from the study team; instead, all depression treatments that participants in this group receive during the study are delivered by their usual providers. The patient's PCP will also receive a letter indicating that their patient has a depressive disorder and was randomized to usual care. This letter will encourage the PCP to follow-up with their patient to address their depression, will note that there are no restrictions on the care that these patients can receive, and will provide the same list of Eskenazi mental health services given to patients. Although this feedback could result in treatment that would not have occurred naturally in primary care, informational support alone is unlikely to improve depression outcomes.¹⁸⁰ Moreover, our pilot trial indicates that depression outcomes achieved with usual care in targeted clinics remain suboptimal (see c2.2). Patients in both arms will continue to have access to services that are part of usual care in the targeted systems. There will be no restrictions on the care received, although new depression treatments received outside of the trial are discouraged in the eIMPACT group.

Assessments

Revision Date: July 13, 2018

	Pre-Treatment* (0 months)	Mid-Treatment† (6 months)	Post-Treatment* (12 months)	Annual Calls‡ (2-4 calls)
Endothelial Dysfunction (Primary Outcome)	X		X	
Atherogenic Physiologic Factors (Secondary Outcomes)	X		X	
Depressive Symptoms (Secondary Outcome)	X	X	X	X
CVD Events (Exploratory Outcome)		X	X	X
Atherogenic Behavioral Factors	X	X	X	X
Conventional CVD Risk Factors	X		X	
Miscellaneous Factors	X	X	X	X

*Clinical Research Center Visit. †Telephone Call.

Endothelial Dysfunction (Primary Outcome)

Patients will undergo FMD assessments at [name] laboratory in accordance with consensus guidelines.⁸¹ [name] as well as [name] and [name] (our vascular ultrasonographers) have undergone certified training through the University of Wisconsin Brachial Artery Reactivity Testing Symposium. Our group has performed 700+ FMD assessments in the past 10 years. We utilize a GE Logiq E ultrasound system with AccessPoint 2011 software. To illustrate the reproducibility of our results, we performed paired FMDs over 1-4 weeks in 11 healthy volunteers in 2013. Intraclass correlations for baseline diameter, reactive hyperemia, and FMD were 0.98, 0.98, and 0.70, which compare favorably to other laboratories.¹⁸¹⁻¹⁸³

After a 10-minute supine rest, high-resolution baseline images of the brachial artery will be obtained from 3 consecutive cardiac cycles. Next, the forearm cuff will be inflated to 250 mmHg for 5 minutes and then rapidly deflated. At 60 and 90 seconds post deflation, images from 3 consecutive cardiac cycles will be acquired. Brachial diameters will be measured at peak R wave. FMD values will be computed as % increase in diameter at 60 or 90 seconds post deflation^{196,197} (the larger of the two values). Percent change in reactive hyperemic flow velocities will also be computed to ensure that sufficient shear stress triggers were induced.

Atherogenic Physiologic Factors (Secondary Outcomes)

To quantify autonomic function, we will assess high-frequency heart rate variability, a parasympathetic index, following established guidelines.^{184,185} See our paper¹⁸⁶ for complete details. Briefly, using an electrode arrangement recommended by Qu et al.,¹⁸⁷ a HIC-2000 impedance cardiograph, and MindWare software, estimates of high-frequency heart rate variability (ln of ms²/Hz) will be derived by spectral analysis (bandwidth: 0.15-0.40 Hz) from 1-minute epochs of ECG data obtained during the last 5 minutes of a 10-minute rest period. To control for the influence of respiration rate on high-frequency heart rate variability, participants will complete a paced-breathing computer task set to a normal resting rate of 12 breaths/minute during ECG data collection. Values will be corrected for respiration.^{188,189} Blood samples obtained by research nurses from the median cubital vein will be centrifuged within 20 minutes. Plasma aliquots will be frozen at -80°C until the time of assay at the Indiana CTSI Clinical Research Assay Laboratory directed by [name]. To quantify systemic inflammation, we will measure IL-6 and CRP levels using R&D Systems ELISA kits. To quantify platelet activation, we will measure levels of platelet-specific release products, β-thromboglobulin (BTG) and platelet factor 4 (PF4),¹⁹⁰ using R&D Systems ELISA kits. The remaining plasma aliquots will be saved for possible future assays. Assistants scoring the autonomic data and performing the assays will be blind to assignment.

Depressive Symptoms (Secondary Outcome)

Like the IMPACT trial,³⁶ we will assess depressive symptoms with 20 depression items of the Symptom Checklist-90 (SCL-20), a reliable and valid measure.¹⁹¹⁻¹⁹⁴ We will examine total score and % remitted. We also added an item ("Sleeping too much") to the SCL-20 to measure this symptom of atypical depression that was not included in the original questionnaire. We will also administer the PHQ-9 to assess depressive symptoms.

CVD Events (Exploratory Outcome)

Our exploratory outcome, modeled after the JUPITER trial,¹⁹⁵ is time to first major CVD event, defined as: CVD death (ICD-10 I20-I25 or I60-I69 the first-listed cause of death); nonfatal MI (CK-MB >3.0 ng/ml, troponin >0.3 µg/L, or ICD-9 410); nonfatal stroke (ICD-9 430-432, 433.01, 433.11, 433.21, 433.31, 433.91, 434.01, 434.11, 434.91); unstable angina requiring hospitalization (inpatient admission ICD-9 411.1); and revascularization – i.e., percutaneous coronary intervention (ICD-9 00.66, 36.03, 36.06, 36.07, 36.09; CPT 92980-92984, 92995, 92996) or coronary artery bypass graft (ICD-9 36.10-36.19; CPT 33510-33536). Because recruitment will occur during Years 01-02, the mean observation period will be 4 years (1-year intervention period plus 3-year follow-

up period), with a range of 3-5 years. The Regenstrief programmer who worked on our IMPACT study³⁵ will identify candidate CVD events by searching the INPC every 6 months (blind to assignment), with the last search performed on the end date. To capture the small number of events that may occur outside of the INPC catchment area, patients will complete a CVD questionnaire at mid- and post-treatment and during the follow-up calls. If a reported event is not in the INPC, we will request medical records from the patient to confirm the event. Our cardiologist ([name]), also blinded, will use standardized criteria to adjudicate all CVD events for this exploratory outcome. [name] has served on endpoint committees for past trials. When needed, [name] will consult with the cardiologist on the DSMB (also blinded). Given that we are coding “harder” events and that many events will be positive for multiple markers, it is unlikely that coded events will be misclassified. We may fail to detect (and thus initially misclassify) a few events through INPC, which is why we are obtaining patient reports and medical records.

Atherogenic Behavioral Factors

The BRFSS Tobacco Use Questionnaire, International Physical Activity Questionnaire, and the Morisky Questionnaire (MMAS-8) will assess tobacco use, physical activity, and adherence to cholesterol and blood pressure medications, respectively. Each scale possesses strong psychometric properties.¹⁹⁶⁻¹⁹⁸

Conventional CVD Risk Factors

SBP and DBP will be the mean of the last 2 of 3 readings.¹⁹⁹ Fasting cholesterol, glucose, insulin, and HbA1c will be quantified using standard methods. BMI will be computed from measured height and weight.

Miscellaneous Factors

